9.1.7. Final Visit

For Cohorts 1 and 2 (Groups 11-13 and Groups 16-18), the visit at 24 months after the first vaccination will be the final visit and include an abbreviated physical examination and vital signs measurement (both at the discretion of the investigator), and recording of any SAEs and associated concomitant medications, and RTIs.^a Blood samples for immunogenicity assessments will be collected. Participants in Groups 14 and 15 (Cohort 2) will continue into a long-term follow-up phase. Their final visit will be the visit at 36 months after the first vaccination.

For Cohort 3, the visit at 36 months after the first vaccination will be the final visit and include an abbreviated physical examination and vital signs measurement (both at the discretion of the investigator), and recording of any SAEs and associated concomitant medications. Blood samples for immunogenicity assessments will be collected.

9.1.8. Early Withdrawal: Early Exit Visit

For participants who are unable to continue participation in the study, but who do not withdraw consent, an early exit visit will be conducted as soon as possible. In the event of early withdrawal from the study, all procedures as required at the final visit (see Section 9.1.7) will be performed. Blood samples for safety laboratory assessments (hematology and biochemistry; Cohorts 1 and 2 only) will be collected if the early exit is within 8 days of the first vaccination. Blood samples for immunogenicity assessments will only be collected if the early exit is at least 14 days after the previous immunogenicity blood draw.

If the early exit visit takes place within 7 days of the previous vaccination, solicited AEs will be recorded; if the early exit visit takes place within 28 days of the previous vaccination, unsolicited AEs will be recorded.

9.1.9. Long-term Follow-up (Groups 14 and 15 from Cohort 2)

Participants in Groups 14 and 15 will continue into the long-term follow-up phase.

^a RTIs will only be recorded during the first 2 RSV seasons of the study (relative to the enrollment date of the first participant in Cohort 1).

Participants will make follow-up visits at the clinic every 6 months (26 weeks) until the final visit at Day 1095. Each visit includes recording of any SAEs related to study vaccine, study procedures, or non-investigational (concomitant) Janssen products, recording of any AEs leading to discontinuation; recording of concomitant medications in conjunction with SAEs related to study vaccine, study procedures, or non-investigational (concomitant) Janssen products, or in conjunction with AEs leading to discontinuation; and collection of samples for cellular and humoral immunogenicity assays.

9.2. Study Evaluations

9.2.1. Immunogenicity

Venous blood samples of approximately 10 mL and 50 mL will be collected for determination of humoral and cellular immune responses, respectively, at the timepoints shown in the [Schedule of Activities](#), or at the early exit visit if the participant prematurely terminates without withdrawing consent (if the early exit is at least 14 days after the previous immunogenicity blood draw).

Venous blood samples (2.5 mL) for transcriptome analysis will be collected on Day 1 (pre-dose), Day 8, and Day 15 in Cohorts 1 and 2.

All sample collection and processing will be performed by the staff at the clinical sites according to current approved standard operating procedures.

It is assumed that all participants will have a pre-existing immune response due to previous RSV exposure.

The humoral and cellular immunogenicity assays that may be used in this study (as available and applicable) are summarized in [Table 16](#) and [Table 17](#) below.

Blood for humoral and cellular immune responses will be drawn from all participants in Cohorts 1 and 2. In Cohort 3, blood will be drawn for humoral immune responses from all participants and for cellular immune responses from a subset of 63 participants.

Immunogenicity samples will be prioritized as outlined in the Laboratory Manual.

Table 16: Summary of Immunogenicity Assays (Humoral)

Assay	Purpose
Primary endpoint (Regimen Selection Cohort [Cohort 2] – Groups 11 to 15 only)	
RSV neutralization A	Analysis of neutralizing antibodies to an A strain
Secondary endpoints	
RSV neutralization A	Analysis of neutralizing antibodies to an A strain
F protein antibodies (ELISA; pre-F and/or post-F)	Analysis of antibodies binding to RSV F protein in pre-fusion and/or post-fusion form
Exploratory endpoints	
RSV strain cross-neutralization	Analysis of cross-neutralizing antibodies to B and/or a different A strain(s)
F protein antibody specificity characterization	Pre- and post-F specificity by binding or functional assays as ELISA, and/or competition ELISA. Adsorption of serum or plasma with pre-F and post-F protein before any antibody assay, epitope mapping, functional VNAs
G and/or N protein antibodies (ELISA)	Analysis of antibodies binding to RSV G and/or N protein
Adenovirus neutralization assay	Analysis of neutralizing antibodies to adenovirus
Functional and molecular antibody characterization	Analysis of antibody characteristics including, but not limited to, ADCC, ADCP, avidity, other respiratory viral neutralizing or binding assays, Ig isotype, functional VNAs to other respiratory viruses, and antibody assessments for antibody repertoire

ADCC: antibody-dependent cell-mediated cytotoxicity; ADCP: antibody-dependent cellular phagocytosis; ELISA: enzyme-linked immunosorbent assay; F: fusion; G: glycoprotein; Ig: immunoglobulin; N: nucleoprotein; RSV: respiratory syncytial virus; VNA: virus neutralizing antibody

Note: Antibody analyses might be performed in nasal samples, serum and plasma.

Table 17: Summary of Immunogenicity Assays (Cellular)

Assay	Purpose
Secondary endpoints	
IFN- γ ELISpot	T-cell IFN- γ responses to RSV F protein peptides
Exploratory endpoints	
ICS	Analysis of T-cell responses to RSV F protein peptide-stimulated PBMC (including, but not limited to, CD4 ⁺ /CD8 ⁺ , IL-2, IFN- γ , TNF- α , activation markers and memory)
Transcriptome analysis	Regulation of genes (clusters), expression patterns, that predict specific immune responses after vaccination
Chemokine/cytokine analysis	Levels of chemokines and cytokines in nasal samples
Sequencing of B-cells	Including but not limited to sequencing of BCR (B-cell receptor) or VH/VL (heavy/light chain characterization) for specificity

ELISpot: enzyme-linked immunospot; F: fusion; ICS: intracellular cytokine staining; IFN- γ : interferon gamma; IL-2: interleukin-2; PBMC: peripheral blood mononuclear cells; RSV: respiratory syncytial virus; TNF- α : tumor necrosis factor alpha

Nasal samples, collected at the timepoints indicated in the [Schedule of Activities](#), will be used for immunogenicity assessments (for example, immunoglobulin or cellular immune component) and identification of the etiology of respiratory infections (if needed).

In addition to RT-PCR performed on nasal samples, any immunogenicity blood sample collected from all participants may also be assayed by serology (including but not limited to RSV VNA or ELISA specific to RSV protein G [glycoprotein] and/or N [nucleoprotein] as available and applicable) for RSV exposure.

Instructions for the collection, handling, storage, and shipment of blood and nasal samples for the immunogenicity assays can be found in the Laboratory Manual that will be provided. Collection, handling, storage, and shipment of samples to the central laboratory must be under the specified, and where applicable, controlled temperature conditions as indicated in the Laboratory Manual.

9.2.2. RTI Procedures

Participants will be informed of the timing of the start and end of the RSV season in accordance with the country/region-specific RSV local surveillance system.

During the first 2 RSV seasons of the study (relative to the enrollment date of the first participant in Cohort 1), participants should record any signs and symptoms of RTI (such as runny nose, fever, severe cough, rapid breathing, difficulty breathing), including measurement of body temperature, on a daily basis until symptoms have resolved using a specific RTI Symptoms Form. Signs and symptoms of RTI recorded on the RTI Symptoms Form will be transferred onto the RTI Symptoms page in the eCRF. RTI Symptoms Forms will be the primary source for RTI monitoring. Participants should complete a new form on each day they experience symptoms, including the day on which the symptoms resolve. Completed RTI forms can either be mailed to the site or brought to the site at the next visit.

If respiratory symptoms develop during the first 2 RSV seasons of the study, the following should take place:

- Participants should contact the site as soon as possible to notify the site of an RTI.
- Participants should record signs and symptoms of the RTI (including measurement of body temperature) daily using the RTI Symptoms Form until the day of symptom resolution.
- If feasible, participants should take a nasal sample at home, preferably between 2 and 3 days after the onset of the RTI symptoms. The sample should be stored refrigerated and brought to the site by the participant within 3 to 4 days.
- Alternatively, participants may go to the site preferably within 2 to 3 days after the onset of the RTI to have a nasal sample taken by the study staff.

The RTI Symptoms Forms and nasal swab kits for use at home will be distributed before the start of the RSV seasons.

During the first 2 RSV seasons of the study, participants will be contacted by telephone every 30±7 days (unless a planned visit has occurred or will occur within 30 days). These calls will remind participants to complete the RTI Symptoms Form in the event of any symptoms of RTI, to contact the site at the time of symptom onset, and to take a nasal sample (or go to the site to have a nasal sample taken by study staff). These calls will also check for any SAEs and associated concomitant medications since the previous visit or telephone contact.

The presence of RSV or any other respiratory infection may be assessed by the sponsor by RT-PCR diagnostics on the nasal samples, which may include viral load and RSV subtyping.

Blood from participants with a suspected RTI may be assayed by a serological assay (eg, protein G and/or N ELISA) to confirm RSV infection. (No additional blood sampling is necessary – any serological assay conducted to confirm RSV infection will use blood from the existing samples.)

Every effort should be made to collect data on the clinical course of RTIs including information on oxygenation status, supplemental oxygen requirements and specific drug treatments, as well as other concurrent respiratory illness present at the time of the diagnosis of the event and up to symptom resolution.

Any RTI that is not due to RSV infection will be reported as an AE if it occurs between the time of any vaccination through the following 28 days. Any RTI recorded as an AE in the eCRF will be excluded from any AE analysis if the central laboratory RT-PCR is subsequently found to be positive for RSV. RTIs arising from RSV infection will not be reported as (S)AEs in the Clinical Study Report as they are endpoints of the study and will be tabulated separately.

Any RTI fulfilling the criteria of an SAE will be reported as such during the entire study period if RT-PCR indicates it is not an RSV-RTI. If the RT-PCR is positive for RSV the event should not be reported as an SAE. If RT-PCR information is not available within 24 hours of knowledge of the event, the event will be reported as an SAE, but will be subsequently downgraded from SAE status if it later turns out to be RT-PCR positive for RSV.

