2. OBJECTIVES, ENDPOINTS, AND HYPOTHESIS

2.1. Objectives and Endpoints

SAFETY COHORT OBJECTIVE (COHORT 1):

To determine in small numbers of participants aged 60 years and older the safety of intramuscular homologous two-dose regimens comprising RSV preF protein or Ad26.RSV.preF/RSV preF protein mixture on Days 1 and 57, with a booster at Month 12, or separate administration of Ad26.RSV.preF and RSV preF protein in opposite arms on Day 1 with a booster at Month 12, before progression to regimen selection in a larger number of participants

Objectives	Endpoints
PRIMARY	

 To assess the safety and reactogenicity of the intramuscular one- and two-dose regimens, with a booster at Month 12 	
 SAEs from first dose administration until the end of the study Solicited local and systemic AEs for 7 days after each vaccine administration Unsolicited AEs from the time of each vaccine administration through the following 28 days
SECONDARY	

 To assess the humoral and cellular immune responses elicited by Ad26.RSV.preF, RSV preF protein, and the Ad26.RSV.preF/RSV preF protein combination and mixture 	
 RSV neutralization assay, F protein binding antibodies (enzyme-linked immunosorbent assay [ELISA]; pre-F and/or post-F), and IFN-γ enzyme-linked immunospot (ELISpot) assay
EXPLORATORY	

 Additional exploratory analyses may be performed to investigate vaccine-elicited immune responses further 	
 Assays to be used include, but are not limited to, RSV strain cross-neutralization, anti-F protein antibody specificity and functionality characterization, adenovirus neutralization assays, molecular antibody characterization (avidity, Fc cell interaction, antibody isotyping, antibody sequencing for repertoire), and nasal antibodies to RSV, including but not limited to immunoglobulin (Ig)A and IgG; evaluation of the cellular immune response and the functional and memory immune response by intracellular cytokine staining (ICS) and transcriptome analysis

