
 To evaluate symptoms of respiratory illness (including respiratory illness due to RSV) via the RTI Symptoms Form 	
 During the RSV season: Signs and symptoms of RTI (including RTI due to RSV) from Day 1 until the end of the second RSV season of the study^a

 Characterization of viral or bacterial infections in the respiratory tract 	
 Assessment, typing and level of infection by RT-PCR or response to respiratory infection by serology

EXPANDED SAFETY COHORT OBJECTIVE (COHORT 3):

To determine the safety and immunogenicity of the selected regimen in an expanded cohort of participants aged 60 years and older; and to determine the need for a booster dose at Month 12 and/or Month 24

Objectives	Endpoints
PRIMARY	

 To assess the safety and reactogenicity of the selected regimen and a booster at Month 12 and/or Month 24 	
 SAEs from first administration until the end of the study Solicited local and systemic AEs for 7 days after each vaccine administration Unsolicited AEs from the time of each vaccine administration through the following 28 days
SECONDARY	

 To assess humoral immune responses to the selected regimen in all participants 	
 RSV neutralization A2 strain

 To assess cellular immune responses to the selected regimen in a subset of participants 	
 IFN-γ ELISpot assay
EXPLORATORY	

 Additional exploratory analyses may be performed to further investigate vaccine-elicited immune responses 	
Assays to be used include, but are not limited to:
 
 F protein binding antibodies (ELISA; pre-F and/or post-F) Flow cytometry RSV cross-neutralization of B and/or other A strain F-protein antibody specificity characterization Cytokines/chemokines in nasal samples (if feasible) Adenovirus neutralization assays

^a The second RSV season of the study is defined relative to the enrollment date of the first participant in Cohort 1.

Objectives	Endpoints
	
 • Functional and molecular antibody characterization • Analysis of nasal antibodies to RSV including, but not limited to IgA and IgG

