11.8. Data Review Committee

Data Review Committee

An internal DRC will be commissioned for this study. The DRC will consist of sponsor personnel not directly involved in the conduct of the study and who have expertise in clinical study conduct and vaccines, at least one medical expert in the relevant therapeutic area, at least one statistician, and a safety expert. The DRC will convene, according to their charter, to discuss any safety issues and any situation meeting a specific study pausing rule (Section 11.9). The PI(s) and SRP/S will inform the DRC of any AE of concern.

In addition, the DRC will review all safety data collected up to the time the final participant in the initial safety cohort (Cohort 1) had his/her Day 8 visit.

It will also be possible for the DRC to review unblinded immunogenicity data during the course of the study if this is deemed necessary for future vaccine development-related decisions. If this is the case, a biomarker representative (not involved in the conduct of the study) will be part of the DRC.

After these reviews, the DRC will make recommendations regarding the continuation of the study. Conclusions of the DRC will be communicated to the investigators, the IRB/IEC and the national regulatory authorities as appropriate. Details will be provided in a separate DRC charter.

If deemed necessary for safety review, the DRC may request randomization codes and review unblinded data, if applicable.

Safety data from the primary analyses and from the analyses at 28 days after the Month 12 booster dose (in Cohorts 1 and 3) and the Month 24 booster dose (Cohort 3 only) will be shared with the DRC.

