11.9. Study Vaccination Pausing Rules

The PI(s) and the SRP/S will monitor the study vaccination pausing rules. If study vaccination is considered to raise significant safety concerns, further study vaccination of participants will be suspended until DRC review is carried out and subsequent communication between the sponsor and the investigator takes place.

The occurrence of any of the following events will lead to pause in further study vaccination and trigger a meeting of the DRC to discuss study suspension, adaptation or discontinuation of further vaccination. The list is only applicable for concerned AEs that occur up to 4 weeks after each vaccination and to concerned SAEs:

1. One or more participants per cohort experience an SAE or other potentially life-threatening (Grade 4) event that is determined to be related to study vaccine; *OR*
2. One or more participants per cohort experience anaphylaxis clearly not attributable to other causes than vaccination with any study vaccine; *OR*
3. Two or more participants per cohort experience a Grade 3 or 4 unsolicited AE of the same type, determined to be related to study vaccine, that persists for 72 hours or longer; *OR*
4. Two or more participants per cohort experience a Grade 3 or 4 solicited systemic AE of the same type, determined to be related to study vaccine, that persists for 72 hours or longer; *OR*
5. Two or more participants per cohort (in Cohorts 1 and 2 only) experience a persistent (upon repeat testing) Grade 3 or 4 laboratory abnormality related to the same laboratory parameter and considered related to study vaccine, that persists for 72 hours or longer; *OR*
6. Death of any participant, considered related to any study vaccine or if the causal relationship to study vaccine cannot be excluded.

Note: All cases of death will be sent to the DRC. Upon their review, the DRC will decide whether a study pause is required.

After the first DRC meeting triggered by the occurrence of a given pausing rule, the DRC will convene thereafter for each additional participant meeting that pausing rule.

The DRC will review blinded data first, but is entitled to and has the right to require submission of unblinded data if deemed necessary.

To enable prompt response to a situation that would trigger pausing rule 3, 4 or 5, the investigator should update the eCRF with information on any Grade 3 or 4 AE on the same day that the AE is reported.

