Also, the investigator should notify the sponsor's medical monitor (and fax/email the SAE Form to Global Medical Safety Operations, if applicable), immediately and no later than 24 hours after becoming aware of any related AE of Grade 3 or above (and update the eCRF with relevant information on the same day the AE information is collected). A thorough analysis of all Grade 3 cases will be carried out by the sponsor's medical monitor, irrespective of whether the criteria for pausing the study are met. Based on the pausing criteria, the sponsor's medical monitor will then decide whether a study pause is warranted. All sites will be notified immediately in the event of a study pause. The sponsor's medical monitor is responsible for the immediate notification of the DRC and coordination of a DRC meeting in the event of a study pause.

Vaccinations for an individual participant may be suspended for safety concerns other than those described in the pausing criteria, at the discretion of the investigator if he/she feels the participant's safety may be threatened. The sponsor's medical monitor or the PI(s) (upon consultation with the sponsor's medical monitor) may initiate a DRC review for any single event or combination of events which, in their professional opinion, could jeopardize the safety of the participants or the reliability of the data.

Vaccinations for the study may be suspended for safety concerns other than those described above, or before pausing rules are met, if, in the judgment of the DRC, participant safety may be threatened.

Resumption of vaccinations will start only upon receipt by the site of written recommendations by the DRC. The clinical site(s) will be allowed to resume activities upon receipt of a written notification from the sponsor. These communications from the DRC will be forwarded by the investigator to the IRB/IEC and by the sponsor to the relevant health authorities according to local standards and regulations.

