Any RTI that is not due to RSV infection will be reported as an AE if it occurs between the time of any vaccination through the following 28 days. Any RTI recorded as an AE in the eCRF will be excluded from any AE analysis if the central laboratory RT-PCR is subsequently found to be positive for RSV. RTIs arising from RSV infection will not be reported as (S)AEs in the Clinical Study Report as they are endpoints of the study but will be tabulated separately.

Serious Adverse Event

An SAE based on ICH and European Union Guidelines on Pharmacovigilance for Medicinal Products for Human Use is any untoward medical occurrence that at any dose:

- Results in death
- Is life-threatening
(The participant was at risk of death at the time of the event. It does not refer to an event that hypothetically might have caused death if it were more severe.)
- Requires inpatient hospitalization or prolongation of existing hospitalization
- Results in persistent or significant disability/incapacity
- Is a congenital anomaly/birth defect
- Is a suspected transmission of any infectious agent via a medicinal product
- Is Medically Important*

* Medical and scientific judgment should be exercised in deciding whether expedited reporting is also appropriate in other situations, such as important medical events that may not be immediately life-threatening or result in death or hospitalization but may jeopardize the participant or may require intervention to prevent one of the other outcomes listed in the definition above. These should usually be considered serious.

If a serious and unexpected AE occurs for which there is evidence suggesting a causal relationship between the vaccine and the event (eg, death from anaphylaxis), the event must be reported as a suspected unexpected serious adverse reaction (SUSAR) by the sponsor to health authorities and by the investigator to the IRB/IEC according to regulatory and local requirements.

Any RTI fulfilling the criteria of an SAE will be reported as such during the entire study period if RT-PCR indicates it is not an RSV-RTI. If the RT-PCR is positive for RSV the event should not be reported as an SAE. If RT-PCR information is not available within 24 hours of knowledge of the event, the event will be reported as an SAE, but will be subsequently downgraded from SAE status if it later turns out to be RT-PCR positive for RSV.

Unlisted (Unexpected) Adverse Event/Reference Safety Information

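### The primary SAE endpoint cannot show non-fatal serious RSV illness once RT-PCR is positive, and the separate output in SAP 5.4 does not specify seriousness

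*Protocol*

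**What the plan says.** **Endpoint.** Protocol 2.1 makes SAEs a primary endpoint in all three cohorts: "SAEs from first dose administration until the end of the study" for Cohorts 1 and 2, and "SAEs from first administration until the end of the study" for Cohort 3.

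**Classification.** Protocol 9.2.2, repeated in 12.1.1 and the synopsis, deals with RTIs that meet SAE criteria: "If the RT-PCR is positive for RSV the event should not be reported as an SAE". If no RT-PCR result is available within 24 hours of learning of the event, it is reported as an SAE and downgraded should the result prove positive. Section 12.1.1 adds: "RTIs arising from RSV infection will not be reported as (S)AEs in the Clinical Study Report". The reason given is that they are study endpoints, and they are to be tabulated separately.

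**Analysis.** Protocol 11.5 and SAP 5.1.1 exclude RTIs recorded as AEs when the central laboratory RT-PCR is RSV-positive. SAP 5.4 summarises participants with confirmed RSV infection, by RT-PCR or serology, per period and group. If there are too few cases, the data are listed.

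**Pausing.** Protocol 11.9 limits the rules: "The list is only applicable for concerned AEs that occur up to 4 weeks after each vaccination and to concerned SAEs". Rule 1 begins: "One or more participants per cohort experience an SAE or other potentially life-threatening (Grade 4) event that is determined to be related" to study vaccine.

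**The concern.** The stated reason for separate handling is that RSV RTIs are study endpoints. In Protocol 2.1 those endpoints are exploratory in every cohort, while SAEs are primary. A primary safety endpoint is therefore thinned in favour of an exploratory one, and the output that replaces it is not designed to show whether an illness was serious.

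This is the first human study of RSV preF protein. Protocol 1.1 recalls that the first RSV vaccine candidate was associated with enhanced respiratory disease on later RSV infection, and says this is not expected in adults already exposed to RSV. The prior risk is low. But serious RSV-positive illness is where such a harm would show, and it is the class of event that the SAE table cannot display by regimen. The same loss of SAE status also affects one route to a pause in dosing.

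**Working it through.** The point concerns classification rules, so the check follows one hypothetical event through them: a non-fatal hospitalisation for an RTI, RT-PCR-positive for RSV, 8 weeks after a dose, judged vaccine-related.

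**Endpoint**

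1. Hospitalisation meets the SAE definition in Protocol 12.1.1.
2. Under 9.2.2 and 12.1.1, a positive RT-PCR means that the event is not reported as an SAE or is downgraded. Relatedness plays no part in that rule.
3. Under 11.5 and SAP 5.1.1, if the event was recorded and the central laboratory confirms RSV, it is left out of the safety and AE analyses.
4. The event is therefore absent from the SAE table for its regimen.
5. SAP 5.4 can count the participant as infected, but it mixes RT-PCR with serological infections and asks for neither seriousness nor relatedness. If it becomes a listing, the contents are not specified.

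**What this does to the plan's detection figures.** Protocol Table 19 gives the chance of seeing at least one event among the 135 + 135 = 270 active Cohort 3 recipients. It reproduces from 1 − (1 − p)^270:

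- p = 0.5%: 1 − 0.995^270 = 74.2% (plan: 74%)
- p = 1%: 1 − 0.99^270 = 93.4% (plan: 93%)

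The arithmetic is right, but it assumes that an event which occurs is counted. For non-fatal, RT-PCR-positive serious RSV illness, the chance of an entry in the SAE table is zero under the rules at any p.

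**Pausing.** The result depends on when RT-PCR reports.

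- *No result within 24 hours.* The event is reported as an SAE. Being related, it meets rule 1. Under 11.9, dosing resumes only on a written DRC recommendation, and nothing there lifts a pause automatically on a downgrade. The pausing rule works.
- *Positive result within 24 hours.* The event is never an SAE. The 9.2.2 sentence does not require the central laboratory, so a hospital result could do this. At 8 weeks it is outside the AE window, so rules 1 and 3 do not reach it. Rules 2, 4 and 5 concern anaphylaxis, solicited systemic events and laboratory values. Rule 6 needs a death. No rule is met.

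The pausing gap thus needs all four conditions: non-fatal, more than 4 weeks after a dose, judged related, and RT-PCR-positive before SAE reporting falls due.

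**The case against.** The strongest reply is that separate handling is deliberate, reasoned and consistent across the synopsis, 9.2.2, 11.5, 12.1.1 and SAP 5.1.1. It keeps the disease that the vaccine is meant to prevent out of the vaccine's AE profile. Safeguards also remain:

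- Under 12.3.2 the cause of any death is an SAE, and under 11.9 all deaths go to the DRC.
- Under 11.9 the investigator should notify the medical monitor within 24 hours of any related AE of Grade 3 or above, and every Grade 3 case is analysed whether or not a pausing criterion is met.
- Under 11.8 the investigators and the study responsible physician or scientist have a duty to inform the DRC of AEs of concern.
- The medical monitor or an investigator "may initiate a DRC review for any single event or combination of events" they think could jeopardise participants' safety.

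All of this stands. A reader might infer that serious RSV illness escapes safety oversight, but the documents do not support that. What can be missing is the automatic pause, not notification. Nor do they show that the DRC is denied these cases. Section 11.8 shares "Safety data from the primary analyses and from the analyses at 28 days after the Month 12 booster dose", and from the Month 24 analysis, but does not say whether the separate RSV tabulation goes with them. The DRC charter is not among the documents.

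A reader might also multiply the care-home infection and pneumonia rates in Protocol 1.1 by the number vaccinated to obtain an event count. That would not measure this problem. Those rates describe frailer people, and they do not give serious, RT-PCR-confirmed or vaccine-related events. RTI surveillance covers only the first two RSV seasons counted from the first Cohort 1 enrolment, and RT-PCR testing is optional. Serious events never tested would remain SAEs.

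The reply does not meet the endpoint point. None of these safeguards puts the event into a table by regimen.

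**Conclusion.** The concern holds in two parts of unequal weight.

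The main part is the endpoint. As specified, the primary SAE tables cannot show non-fatal, RT-PCR-positive serious RSV illness by regimen, and SAP 5.4 is not designed to restore it. It would go too far to say that the information can never be recovered: a listing is possible, and 9.2.2 asks for clinical-course data such as oxygen needs and treatment. The plan simply does not commit to showing seriousness.

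The smaller part is the pausing gap, confined to the four conditions above.

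The size is structural: a zero contribution to the SAE count at any true rate. The documents give no usable figure for how many events would be affected. The conclusion assumes that the rules are applied as written. It is limited to non-fatal events because the blanket wording of 9.2.2 sits awkwardly with the death rule in 12.3.2. This is a worthwhile, inexpensive improvement, and it does not undermine the trial's design.

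**What to change.** **SAP 5.1.1.** Present participants with any SAE by regimen twice: without and with RSV RT-PCR-positive RTIs that meet SAE criteria. The first row keeps the sponsor's planned view.

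**SAP 5.4.** Show RT-PCR-confirmed RSV RTIs separately from serology-only infections, with the number meeting SAE criteria and the number judged related. Give these counts to the DRC with the data named in Protocol 11.8.

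**Protocol 9.2.2 and 12.1.1, with the matching synopsis text.** Record seriousness and relatedness in the eCRF for every RSV-positive RTI. State that one meeting SAE criteria and judged vaccine-related counts for pausing rule 1. Non-serious RSV RTIs can stay out of the AE tables as planned.

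**Cost.** The extra collection is a seriousness and a relatedness field, needed chiefly where a same-day positive result means that no SAE form is filed. SAP 5.1.1 gains one or two table rows and SAP 5.4 a split with two counts. There may be a few more DRC reviews, and possibly expedited reports if a related event is treated as serious. If a protocol amendment is no longer practical, the SAP changes are still worth making with whatever seriousness data exist.
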